- 9. Have history of relapse and/or exacerbation of symptoms when they were not receiving antipsychotic treatment, according to the Investigator's opinion.
- 10. Patients willing to discontinue all prohibited psychotropic medications prior to Screening, if determined to be clinically appropriate by the Investigator, and not for the sole purpose of inclusion in the trial.

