- 21. Clinically significant abnormal finding on the triplicate set of ECGs or evidence of any of the following cardiac conduction abnormalities at Screening (mean values will be used for the following criteria):
 - Heart rate <40 beats per minute (bpm) and >110 bpm (based on the ECG reading). NOTE: The Medical Monitor should be contacted in any instance where the Investigator is uncertain regarding the stability of a patient's medical condition(s) and the potential impact of the condition(s) on trial participation
 - Interval between Q and T wave corrected for heart rate using Fridericia's formula (QTcF) interval >450 msec for males and females
 - PR interval ≥200 msec
 - Intraventricular conduction delay with QRS duration >120 msec
 - Evidence of second- or third-degree atrioventricular block
 - Electrocardiographic evidence of complete left bundle branch block (LBBB), complete right bundle branch block (RBBB), or incomplete LBBB

Prohibited Therapies or Medications

- 22. Patients who are currently taking oral antipsychotic medications, monoamine oxidase inhibitors (MAOIs), anticonvulsants (e.g., lamotrigine, Depakote), tricyclic antidepressants (e.g., imipramine, desipramine), selective serotonin reuptake inhibitors, and any other antidepressants or any other psychoactive medications (except lorazepam, zolpidem, zaleplon, eszopiclone, or similar benzodiazepines, diphenhydramine, benztropine, and propranolol). Patients taking prohibited psychotropic medications may be eligible for inclusion in the study if it is clinically appropriate to discontinue the medication before the Baseline Visit (in the opinion of the Investigator). The prohibited psychotropic agent must be discontinued and washed out at least 5 half-lives prior to Baseline. Subjects taking a depot antipsychotic could not have received a dose of medication for at least 1 and a half injection cycles before Baseline. The medications should not be discontinued solely to make the patient eligible for enrollment in the study.
- 23. Patients who received electroconvulsive therapy within 90 days of Screening.
- 24. Patients who received Transcranial Magnetic Stimulation (TMS) within 90 days of Screening.

Confidential Page 42 of 102

Allergies and Adverse Drug Reactions

- 25. Patients with a history of neuroleptic malignant syndrome.

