6.7 Prior and Concomitant Medications

All prescription, nonprescription medications (e.g., over-the-counter [OTC]) drugs and herbal supplements) and non-medical treatments starting from 30 calendar days before Screening until end of the study must be recorded in source documents and the eCRF. For each medication, documentation should list the trade or generic name, the total daily dose including units (or the dose, units, and scheduled and actual frequency of administration if the medication is not taken daily), the route of administration, and the reason for use.

Changes, additions, or discontinuations to medications will be assessed and recorded in the eCRF during each study visit. All as-needed prescriptions should be converted to reflect actual dose taken per day.

Starting on the first day of the screening phase, after written informed consent for the study has been provided, all antipsychotic or other psychotropic medications will be stopped with clinically appropriate titration down as per the Investigator's clinical judgment. Patients will be

Confidential Page 49 of 102

instructed not to take any medication(s) during the conduct of the study unless approved by the Investigator. Any patient unable to be safely discontinued from current antipsychotic therapy or other psychotropic medications will not be eligible for the study. Any treatment other than the study treatment given will be considered a concomitant medication and will be documented in the eCRF. Any patient requiring emergency treatment with prescription or nonprescription medication during the screening phase through the EoS Visit will be approved by the Investigator. If the Investigator determines that the patient requires medication during the study, the Medical Monitor must be contacted within 24 hours.

Psychotropic medications are prohibited except for lorazepam as needed for agitation, restlessness, irritability, or hostility; zolpidem, zaleplon, or eszopiclone for insomnia; diphenhydramine or benztropine for EPS; and propranolol for akathisia.

Within the daily limits shown in 2, lorazepam, benztropine, and propranolol are not allowed on as needed basis; every administration must be considered and approved by the Investigator prior to administration.

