Vital Signs ^t	X	X		X		X		X		X		
Adverse Events ^u	X	X	X	X	X	X	X	X	X	X	X	X
Other												
Study Drug Dosing		X	X	X	X	X	X	X	X	X		
PK Sample Collection ^v		X		X				X				
Restart Standard Antipsychotic ^w											X	

a. Screening begins when the ICF is signed and will take place between Day -7 and Day -1; up to a 7-day extension of the screening phase is allowed, if necessary with the approval of the Medical Monitor; screening procedures should be initiated with a sufficient amount of time allotted in order to obtain central laboratory results and ECG results from the central reader prior to randomization. Review of inclusion/exclusion criteria at Baseline will be based on assessments performed during Screening. Hospitalization will begin with the signing of the ICF for patients who are not already hospitalized at the initial Screening Visit.

Confidential Page 55 of 102

Each patient may receive the QD administration of study treatment. No other assessments are scheduled; however, AEs observed or reported, and concomitant medications may be recorded. In case of an AE, an unscheduled visit may be conducted at the discretion of the PI.

c. Stabilization Period is up to 5 days.

d. The Screening assessments to be audio recorded include the MINI 7.0.2, PCRS and SCI-PANSS and are submitted to an independent central reviewer for review and eligibility confirmation.

^{e.} Includes full psychiatric history, DSM-5 diagnosis of schizophrenia, and MINI 7.0.2.

Washout of prohibited medications begins after signing the ICF and after diagnosis of Schizophrenia is confirmed by MINI. Details of medications requiring washout and guidance for washout time required are provided in Appendix 14.4. Prohibited and restricted medications are listed in Table 6.3:

g. Urine drug screen (full panel including opioids) and a blood alcohol test are required at the designated times, but either or both can be conducted at any time during the trial at the discretion of the Investigator.

h. At Screening, Baseline, and final endpoint, SCI-PANSS and CGI-S will be evaluated by a local site rater with central supervision via independent, central review.

SCI-PANSS will be audio recorded at any visit where they are administered. SCI-PANSS assessment should be preceded by the PCRS. Patients with improvement of ≥20%

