7.2 Study Procedures by Time Point

7.2.1 Visit 1 (Screening – up to 7 Days)

The Screening Visit is to occur within 7 calendar days prior to the start of study drug administration. After the patient has signed the ICF, the following assessments will be performed and recorded in the patient's source documentation/medical record and in the eCRF:

- Administration of informed consent
- Subjects will also be asked to provide additional consent for their participation in a secure, proprietary research subject database administered by Verified Clinical Trials ([VCT], Garden City, NY). The database will utilize partially identified subject information to review subjects' research study history within the database. Participants who are identified as verification failures by VCT, should not be enrolled without documented approval from LB Pharmaceuticals

 At the last subject contact, VCT staff will automatically close out the subject (safety follow-up, ET, or complete) based on the Interactive Response System (IXRS)
- Admission to inpatient unit
- DSM-5 diagnosis of schizophrenia
- MINI 7.0.2
- MINI-Plus BPD 7.0.2
- Review of inclusion and exclusion criteria
- Recording of medical history
- Recording of prior and current medications (e.g., prescription and nonprescription medications)
- Washout of prohibited psychotropic medications (after signing of ICF)
- PANSS, PCRS must be administered before PANSS
- CGI-S
- C-SSRS
- Collection of demographic information
- Physical examination including height
- Body weight, BMI (derived programmatically from body weight and height measurements), and waist circumference
- Vital signs
- Resting 12-lead ECG (triplicate, further information in Section 8.2.3)

Confidential Page 58 of 102

- Collection of blood and urine samples for clinical laboratory tests. Lab results that are exclusionary are presented in Table 14.2 and other information is presented in the footnotes to the SoA (Table)
- Urine pregnancy test for all females of childbearing potential
- Assessment and recording of AEs
- Urine drug screen/blood alcohol test
- AIMS
- BARS
- SAS
- Submission of applicable data to the Endpoint Adjudication Committee for confirmation of eligibility
- Cogstate test practice assessment

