14.4 Half-Life of Major Psychiatric Medications

The recommended duration of the washout period should be $5 \times$ the duration of the known half-life of the drug.

Half-life after oral administration (hours)
75-94
24
91
48-96 (parent drug) 7-21 days (active metabolites)
12
18-26
29-37 (at steady state)
30-38
23
57 parent drug (200 for active metabolite)
6-12
20
7 oral 2-5 IM
30
33
20
6-8 (parent drug) 12 (active metabolites)
9-12 (parent drug) 10-19 (active metabolite)
55
34

Confidential Page 100 of 102

Thioridazine	4-10 (parent drug)
	21-25 (active metabolites)
Trifluoperazine	3-12 (parent drug)
	22 (active metabolites)
Antidepressants	
Selective Serotonin Reuptake Inhibitors (SSRI)	
Citalopram	20-30
Escitalopram	
Paroxetine	
Sertraline	
Fluoxetine	1-3 days
Fluvoxamine	15
Serotonin-norepinephrine (SNRI) reuptake inhib	itors
Desvenlafaxine	9-11
Duloxetine	10-12
Levomilnacipran ER	12
Milnacipran	8-10
Venlafaxine	5 (parent)
	11 (active metabolites)
Tricyclics	
Amitriptyline	9-25
Imipramine	19
Clomipramine	12-36
Doxepin	3-80
Nortriptyline	36
Monoamine oxidase inhibitors (MAOIs)	
Tranylcypromine	2
Phenelzine	12
Isocaroxazid	36
Moclobemide	2-4
Other	
Mirtazapine	20-40

Confidential Page 101 of 102

	·
Agomelatine	1-2
Reboxetine	13
Vortioxetine	66
Benzodiazepines	
Alprazolam	12-15
Lorazepam	10-20
Oxazepam	6-20
Diazepam	36-200
Chlordiazepoxide	3 -200
Temazepam	5-15
Nitrazepam	24-40
Non-Benzodiazepine Anxiolytics	
Buspirone	2-11
T T	
Pregabalin	6
-	
Pregabalin	
Pregabalin Antiepileptics	6
Pregabalin Antiepileptics Carbamazepine	12-27
Pregabalin Antiepileptics Carbamazepine Gabapentin	6 12-27 5-7
Pregabalin Antiepileptics Carbamazepine Gabapentin Lamotrigine	6 12-27 5-7 15-35
Pregabalin Antiepileptics Carbamazepine Gabapentin Lamotrigine Levetiracetam	6 12-27 5-7 15-35 6-8
Pregabalin Antiepileptics Carbamazepine Gabapentin Lamotrigine Levetiracetam Oxcarbazepine	6 12-27 5-7 15-35 6-8 8-15
Pregabalin Antiepileptics Carbamazepine Gabapentin Lamotrigine Levetiracetam Oxcarbazepine Pregabalin	12-27 5-7 15-35 6-8 8-15 5-7
Pregabalin Antiepileptics Carbamazepine Gabapentin Lamotrigine Levetiracetam Oxcarbazepine Pregabalin Topiramate	12-27 5-7 15-35 6-8 8-15 5-7 20-30

Confidential Page 102 of 102

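### For a patient still taking certain drugs at consent, the five-half-life washout cannot fit the 14-day Screening maximum, and the protocol gives two different times for stopping medication

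*Protocol*

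**What the plan says.** **When medication stops.** Inclusion criterion 10 (Protocol Section 5.1) describes "Patients willing to discontinue all prohibited psychotropic medications prior to Screening". Three other places put washout after consent:

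- Section 6.7: "Starting on the first day of the screening phase, after written informed consent for the study has been provided, all antipsychotic or other psychotropic medications" are to be stopped, with "will be stopped with clinically appropriate titration down as per the Investigator's clinical judgment" describing how.
- Section 7.1, washout footnote: "Washout of prohibited medications begins after signing the ICF and after diagnosis of Schizophrenia is confirmed by MINI".
- Section 7.2.1, Visit 1 list: "Washout of prohibited psychotropic medications (after signing of ICF".

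The Section 7.1 footnotes also define Screening as starting when the consent form is signed.

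**How much time there is.** Sections 4.1, 4.2 and 7.1 give a 7-day Screening phase and an extension of up to 7 days with Medical Monitor approval.

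**How much time is needed.** Exclusion criterion 22 (Section 5.2) says: "The prohibited psychotropic agent must be discontinued and washed out at least 5 half-lives prior to Baseline". Section 5 permits no deviation from the eligibility criteria. Appendix 14.4 repeats the five-half-life rule as a recommendation and lists half-lives. Some rows carry two values, for example "48-96 (parent drug) 7-21 days (active metabolites".

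**The concern.** The start of washout, the length of Screening and the required time off drug are set in separate places, and for some listed drugs they cannot all be met. If washout starts only after consent, a patient taking a long-half-life drug at that moment can have it withdrawn in hospital during an acute exacerbation. That patient then reaches the end of the longest permitted Screening still ineligible under criterion 22. The plan does not say what happens next, or ask anyone to establish before stopping the drug whether the washout can finish in time.

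Inclusion criterion 10 does not resolve this. Read literally, it moves discontinuation ahead of consent, which conflicts with the other three places.

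**Working it through.** **Step 1: confirm the 14-day maximum.** Section 7.1 gives a maximal individual duration of about 8 weeks, with the last visit on Day 42. Extended Screening plus Day 42 is 7 + 7 + 42 = 56 days, and 56 / 7 = 8.0 weeks. The plan's own figure is reproduced, so 14 days is the intended maximum.

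**Step 2: the longest half-life that fits.** Five half-lives fit a window of W days if the half-life is at most W × 24 / 5 hours.

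- Standard Screening: 7 × 24 / 5 = 33.6 h.
- With the full extension: 14 × 24 / 5 = 67.2 h.
- Each day spent on down-titration lowers the limit by 24 / 5 = 4.8 h.

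**Step 3: apply this to Appendix 14.4.** Days needed = 5 × half-life in hours / 24.

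| Listed half-life | Days needed | Fits in 14 days? |
|---|---|---|
| 75–94 h | 15.6–19.6 | Never |
| 91 h | 19.0 | Never |
| 48–96 h (parent) | 10.0–20.0 | Lower end only |
| 7–21 days (active metabolites of the same row) | 35–105 | Never, if metabolites count |
| 57 h (parent) | 11.9 | Yes, with the extension |
| 200 h (active metabolite of the same row) | 41.7 | Never, if metabolites count |

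The shortest result for the first two rows, 15.6 days, would still not fit if the window were counted one day more generously. The 57 h parent row fits with 14 − 11.9 = 2.1 days left for any titration. Among the named antidepressants, fluoxetine (up to 3 days, so 15.0 days) and doxepin (up to 80 h, so 16.7 days) exceed 14 days at their upper values only.

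**Step 4: which half-life counts.** Exclusion 22 speaks of the agent and Appendix 14.4 of the drug, yet the appendix also lists active metabolites. For one row that choice moves the answer from 11.9 to 41.7 days. For another it moves it from 10–20 to 35–105 days.

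**Limit of the source.** Drug names for the tabulated rows did not survive text extraction. Their position ahead of the antidepressant heading, in a list ending with thioridazine and trifluoperazine, suggests that they are antipsychotics. That is an inference.

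**The case against.** The strongest reply is that an exclusion which some patients cannot meet is not an error: such patients simply fail screening. Criterion 22 counts back from Baseline, so time off drug before consent counts, and most listed drugs fit within 14 days. Checks also exist:

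- The washout footnote directs sites to Appendix 14.4.
- Medications are recorded from 30 days before Screening.
- Eligibility is reviewed at Screening and again at Baseline.
- Discontinuation must be clinically appropriate and not solely for eligibility.
- Patients who cannot safely stop are ineligible.
- Section 4.1 allows re-screening case by case.

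Much of this stands. It confines the problem to patients still taking one of a few drugs at consent, and it rules out saying that nothing is checked. But the safeguards test clinical suitability; none asks for a comparison of dates before the drug is stopped. Re-screening is discretionary and does not make the washout achievable on the first screening.

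Inclusion 10 might also be read as requiring willingness, not discontinuation, before Screening. That would ease the timing conflict but leave the window arithmetic unchanged.

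A reader might see three conflicting start times. The documents support two: Section 6.7 and the footnote are compatible, because the MINI is itself a Visit 1 procedure.

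**Conclusion.** The point holds in a limited form. On any reading of Appendix 14.4, the rows at 75–94 h and 91 h need 15.6–19.6 days against at most 14, if the drug is still being taken at consent and washout starts then. The 48–96 h parent row fails at its upper end. In these cases following the plan can mean withdrawing a drug for a washout that cannot be completed on that screening. The documents give no figure for how many patients this affects.

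Two stronger readings are tempting and not supported:

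- **That washout takes up to 105 days as a settled fact.** The 35–105 and 41.7 day figures depend on counting active metabolites, which the documents do not decide.
- **That residual drug would narrow the treatment contrast.** This requires a site to randomize against criterion 22, although Section 5 permits no deviations. For the two rows that fail on any reading, first-order decay leaves 2^(−336/75) = 4.5% to 2^(−336/94) = 8.4% after 14 full days, against 2^(−5) = 3.1% at five half-lives. Nothing in the documents links that difference to an effect on PANSS.

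**What to change.** Reconcile inclusion criterion 10, exclusion criterion 22, Section 6.7, the Section 7.1 washout footnote, the Section 7.2.1 list, Appendix 14.4 and the Screening maximum. The start of washout, the available window and the five-half-life requirement should be achievable together. State whether the parent or the active-metabolite half-life counts.

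Then have the existing Screening and Baseline eligibility reviews compare two dates: the last-dose date plus the protocol's own required washout, and the latest permitted Baseline date. Which clinical rule to adopt is for the sponsor; none is proposed here.

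The cost is amendment wording and one date comparison on the eligibility form. Some patients would be recognized as unable to complete the washout at the start of Screening instead of after up to two weeks in hospital.

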in total PANSS score between the Screening and Baseline assessments will be excluded from study participation. SCI-PANSS will be administered first on visits before any other scales, when SCI-PANSS and CGI-S are being administered with the exception of Screening where MINI-Plus BPD 7.0.2 will be administered first.

The Placebo-Control Reminder Script[©] Hassman and Cohen, 2019, Version 5.0 educates clinical trial subjects of key causes of the placebo and nocebo effects, level setting of the subject's study expectations, reminding subjects what a placebo is and how that relates to their reporting of symptoms and potential side effects, and explaining how interactions with research site staff differ from their experience with clinical providers. The PCRS informs subjects that they are to be honest about their symptoms and that the site staff have no expectations of symptom improvement or worsening and will not be disappointed by the subject's responses, and asks subjects to explain in their own words PCRS content to ensure comprehension. The PANSS Rater will read the PCRS before administering the PANSS at each study visit.

- During Screening, patients will undergo a practice assessment of the Cogstate test. On Day 1 and Day 28, the actual Cogstate testing will be performed. Note: Cogstate Battery test creot be done within 8 hours of receiving a benzodiazepine or sleep medication.
- To include height at the Screening Visit only. A full physical examination will be conducted at the Screening Visit and at EoT Visit. At each other study visit, patients will be assessed for continued dosing and any possible physical symptoms and a targeted physical examination may be performed, if indicated.
- k. On Days 1, 8, 15, 21, and 28, the SAS, BARS, and AIMS assessments are to be conducted 3 to 6 hours after the administration of study treatment with the exception of ET Visit.
- 1. If the administration of C-SSRS at Screening highlights the risk of suicide not previously known, in the opinion of the Investigator, the patient should be excluded from the trial. At this visit the "Baseline/Screening" version of the C-SSRS scale will be used.
- m. At all other study visits the "Since Last Visit" version of the C-SSRS scale should be used.
- ^{n.} BMI; derived programmatically from body weight and height measurements.

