7.2.2 Visit 2 (Baseline, Study Day 1)

At this visit, the following assessments will be performed and recorded in the patient's source documentation/medical record and in the eCRF:

- Review of inclusion and exclusion criteria
- Recording of concomitant medications (e.g., prescription and nonprescription medications)
- Targeted physical examination (if applicable)
- Body weight, BMI (derived programmatically from body weight and height measurements), and waist circumference
- Vital signs
- Resting 12-lead ECG (triplicate, further information in Section 8.2.3)
- Collection of blood and urine samples for clinical laboratory tests. Additional information is presented in the footnotes to the SoA (Table)
- Urine pregnancy test for all females of childbearing potential
- Assessment and recording of AEs
- PANSS- patients with improvement of ≥20% in total PANSS score between the Screening and Baseline assessments will be excluded from study participation. PCRS must be administered before PANSS
- CGI-S
- C-SSRS
- Randomization
- Pre-dose PK blood sample will be collected
- Study drug administration

Confidential Page 59 of 102

- PK sample collection for the first 60 patients randomized regardless of cohort at the following timepoints after the morning dose: 15 minutes, 30 minutes, 1, 2, 3, 4, 8, and 24 hours
- AIMS, 3 to 6 hours post-dose
- BARS, 3 to 6 hours post-dose
- SAS, 3 to 6 hours post-dose
- Cogstate test

7.2.3 Study Days 2 Through 7

On Days 2, 3, 4, 5, 6, and 7 each patient may receive the QD administration of study treatment. No other assessments are scheduled; however, AEs observed or reported, and concomitant medications may be recorded. If any assessments are required in order to evaluate an AE, an unscheduled visit may be conducted, at the discretion of the PI.

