8.1.1.5 Cogstate Computerized Battery of Tests

The Cogstate Computerized Schizophrenia Battery of Tests is a measure of cognitive ability in subject with Schizophrenia in both the acute and chronic stages and will take approximately 22 to 35 minutes to complete. Patients will have 1 practice session during the Screening Visit and complete the actual test on Day 1 (Baseline) and Day 28 (Visit 6) ET Visit). For each Cogstate test, the construct validity for cognitive impairment in Schizophrenia and sensitivity to change in cognition in such patients have been demonstrated in scientific literature. Patients perform the test on a provided laptop and then it is uploaded via a web-based portal.

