### 5.2.2 Baseline

Baseline is defined as the last non-missing value (either scheduled, unscheduled, or repeat) before the patient receives the first dose of study drug.

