### 5.11.6.1 Effect of LB-102 on Cogstate test scores

Summaries for the actual and change from Baseline values for each of the Cogstate test scores (International Shopping List Test, Detection Test, Identification Test, One Back Test and Modified Groton Maze Learning Test) will be provided by treatment group. In addition, an analysis of covariance (ANCOVA) model will also be fit including pooled study site and treatment as categorical covariates and baseline Cogstate test score as continuous covariate and change from baseline to day 28 in the Cogstate test score as the response. LS means and their differences alongside 95% CIs and p-values for the comparison of active arms vs placebo will be reported. The following sample SAS code will be used:

```
ods output estimates = est LSMeans = lsm diffs = diff;
proc mixed data =  plots (only) = studentpanel(marginal);
  by test;
  class trt01pn siteid;
  model chg = trt01pn siteid base / ddfm = kr;
  lsmeans trt01pn / diff cl;
run;
```

All Cogstate test score results will also be listed.

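### The Day 1 Cogstate test has no stated timing relative to the first dose, so the pre-dose Baseline rule can select the Screening practice run or leave no baseline

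*Protocol*

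**What the plan says.** **Role of each test.** The Cogstate footnote in Protocol 7.1 reads: "During Screening, patients will undergo a practice assessment of the Cogstate test. On Day 1 and Day 28, the actual Cogstate testing will be performed". The Screening list in 7.2.1 accordingly has "Cogstate test practice assessment" as an item, and Protocol 8.1.1.5 labels the Day 1 test as Baseline.

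**Day 1 order.** In Protocol 7.2.2, "Study drug administration" follows randomization and the pre-dose PK sample. Then come the post-dose PK samples, AIMS, BARS and "SAS, 3 to 6 hours post-dose". The last item is "Cogstate test", with no timing label.

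**Baseline rule.** SAP 5.2.2 reads: "Baseline is defined as the last non-missing value (either scheduled, unscheduled, or repeat) before the patient receives the first dose of study drug". Protocol 10.1 likewise restricts Baseline to observations made before study medication starts. Neither has a separate rule for Cogstate.

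**Use of the baseline.** The ANCOVA in SAP 5.11.6.1 takes "baseline Cogstate test score as continuous covariate and change from baseline to day 28 in the Cogstate test score as the response". Protocol 10.4.4.4 rules out imputation for this endpoint.

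**The concern.** The protocol intends the Day 1 test to be the reference for change in cognition. The analysis rule picks the baseline by its time relative to the first dose, and the protocol does not fix that time for Cogstate. A site can test after dosing without deviating from the protocol, and the intended baseline then fails the SAP's own definition.

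The baseline enters the model twice, as covariate and as the subtracted value in the change score, so the wrong record affects both. If sites differ in timing, one analysis could combine patients referenced to a Day 1 test, patients referenced to a practice session, and patients lost for want of a baseline. The practice session may be up to 7 days before Day 1, or up to 14 days (7 + 7) with the permitted screening extension. Since washout starts only after consent and confirmation of diagnosis, the session may also fall before washout is complete. Analysts cannot recover a pre-dose test that was never done.

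**Working it through.** There is no figure in the plan to reproduce. The check is a cross-reading of the timing text against the Baseline rule.

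**Step 1: is the Day 1 test timed against the dose anywhere?**

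| Place | Timing given for Cogstate |
|---|---|
| Protocol 7.1, Cogstate footnote | Day 1 and Day 28; 8-hour gap after a benzodiazepine or sleep medication |
| Protocol 7.2.2 | Last item on Day 1, unlabelled |
| Protocol 8.1.1.5 | Day 1, labelled Baseline |
| Protocol Table 6.2 | 8-hour gap after sleep medication |

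None of these refers to study drug.

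**Step 2: does the Baseline label itself make the test pre-dose?** No. Baseline is also the name of Visit 2. At that visit AIMS, BARS and SAS are explicitly 3 to 6 hours after dosing, so an assessment can belong to the Baseline visit and still be post-dose.

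**Step 3: apply SAP 5.2.2 literally to each case.**

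| Day 1 test | Practice result stored? | Baseline under the rule |
|---|---|---|
| Before first dose | Either | Day 1 actual test, as intended |
| After first dose | Yes | Screening practice result |
| After first dose | No | None |

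**Step 4: carry each case into the ANCOVA.** In the first row the analysis works as planned. In the second, the practice score is both covariate and reference for change. In the third, covariate and change score are both missing; with no imputation, the patient leaves the model.

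**Step 5: would using the Day 1 post-dose value instead solve it?** No. It contradicts both Baseline definitions. In Protocol Table 14.1, the single-dose median Tmax was 3 hours at 50 mg and 3.01 hours at 100 mg. A test done alongside the 3-to-6-hour scales could therefore fall near peak exposure in the active arms.

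**The case against.** The best counter-argument is that the documents have one coherent reading. The protocol labels the Day 1 test Baseline and defines Baseline as pre-dose, so the test must be pre-dose, and only an operational label is missing. Where the protocol wants post-dose testing it says so, as for AIMS, BARS and SAS. List order also proves little: the PK item runs to 24 hours yet precedes the 3-to-6-hour scales, and Cogstate also closes the Screening, Day 28 and early termination lists. Nothing says that practice results are scored or stored.

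Much of this stands. A pre-dose test is probably what was meant, and bullet order is not stated to be chronological. A reader might infer from the list that every patient would be tested after dosing; the text does not support that.

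The argument does not close the gap. The label cannot carry the timing when other assessments at the same visit are post-dose by instruction. PANSS and CGI-S also lack a pre-dose label, but they precede randomization in the list and bear on Day 1 eligibility, including the exclusion for 20% improvement in PANSS. Cogstate has no such anchor. If practice results are not stored, the outcome for a patient tested after dosing is a missing baseline, which is no better.

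**Conclusion.** The point holds as a gap between the visit schedule and the Baseline rule. The protocol permits a post-dose Day 1 Cogstate test, and for any patient tested that way the rule selects the practice result or leaves no baseline.

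**Size.** Only the exploratory Cogstate analysis is affected. The primary and secondary endpoints and the Hochberg procedure are untouched. The number of patients depends on site practice and cannot be derived; it is zero if every site tests before dosing.

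**Assumptions.** Whether a patient gets a practice baseline or a missing one depends on whether practice results reach the database, which the documents do not say.

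**Stronger readings not supported.** A reader might infer that learning effects would bias the comparison with placebo. The documents do not state the purpose of the practice session. If it is for familiarization (an assumption), a practice baseline would put some of that gain into change scores in all arms. Treatment is randomized and blinded, and nothing suggests that test timing would differ by arm. Added noise or a weaker covariate is plausible, but its size cannot be derived.

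**What to change.** **Protocol 7.2.2 and the Cogstate footnote:** reconcile both with the pre-dose Baseline definition by stating that the Day 1 Cogstate test is completed before the first dose.

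**SAP 5.2.2:** add a Cogstate rule with three parts.
- The baseline is the Day 1 actual test taken before the first dose.
- The Screening practice result is never a baseline.
- A Day 1 test taken after dosing is flagged and not used as Baseline in the main ANCOVA; a sensitivity analysis may include it.

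The condition that the test precedes the first dose is essential. A sentence making the Day 1 test the baseline unconditionally would admit post-dose values against Protocol 10.1 and SAP 5.2.2. Applying the rule needs the times of the Day 1 test and of the first dose.

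**Cost:** a short SAP addition and a protocol clarification, with no extra test. The battery takes about 22 to 35 minutes (Protocol 8.1.1.5), so Day 1 scheduling before dosing becomes slightly tighter. A few patients tested late may be lost from the main Cogstate analysis.
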